## 9.4. Presentation of PK data

### 9.4.1. Handling of Dropouts, Missing Data

Missing concentration data for all patients who are administered study drug will be considered as non-informative missing and will not be imputed. No concentration estimates will be provided for missing sample values.

The sampling time of predose samples relative to dosing will also be treated as zero; if the actual time of sampling is missing, the planned time can be used.

This document is confidential.

#### 9.4.2. Handling of BLQ and ULOQ

For calculation of PK parameters, summary statistics and individual serum concentration vs time curves of total IgG, IgG subclasses (sp serotypes) and specific antibodies (anti-Haemophilus influenza type b, anti-pneumococcal capsular polysaccharide, and anti-Tetanus toxoid) following rules will be applied if values are below lower limit of quantification (BLQ) or above upper limit of quantification (ULOQ):

1. All the ULOQ values will be imputed to the highest limit of quantification
2. During the full PK profile curves (visit 5 and 7), If there are more than 4 ULOQ value in the curve, values will be imputed as above, but no PK parameters will be calculated for that visit.
3. All the BLQ values will be imputed to BLQ/2.
4. During the full PK profile curves (visit 5 and 7), If there are more than 4 BLQ value in the curve, values will be imputed as above, but no PK parameters will be calculated for that visit.

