## 1. Glossary of Abbreviations

Abbreviation	Description
ADR	Adverse Drug Reaction
AE	Adverse Event
AIC	Akaike's information criterion
ATC	Anatomical Therapeutic Chemical
AUC	Area under the concentration-time curve
AUC (0-inf)	Area under the concentration-time curve from time zero extrapolated to infinity
AUC 0-t	Area under the plasma concentration vs. time curve from time 0 to the time t of the last quantifiable concentration
AUC tau	Area under the concentration-time curve calculated from start to end of the dosing interval
BLQ	Below Limit of Quantification
BMI	Body Mass index
C avg	Average concentration
CI	Confidence Interval
CL ss	Steady-state clearance
C max	Maximum concentration
C min	Minimum concentration
CRF	Case Report Form
CTCAE	Common Terminology Criteria for Adverse Events
CV	Coefficient of Variation
DRM	Data Review Meeting
DSMB	Data Safety Monitoring Board
ECG	Electrocardiogram
EMA	European Medicines Agency
FAS	Full Analysis Set
FDA	Food and Drug Administration
GCP	Good Clinical Practice
ICH	International Conference on Harmonization
Ig(s)	Immunoglobulin(s)
IVIg	Intravenous Immunoglobulin

This document is confidential.

Abbreviation	Description
$K_{el}$	Elimination constant
KIg10	Kedrion intravenous immunoglobulin 10%
$\lambda_z$ (lambda z)	Terminal elimination rate constant
Max	Maximum
MedDRA	Medical Dictionary for Regulatory Activities
Min	Minimum
MSB	Between-groups mean squares
MSW	Within-groups mean squares
MI	Multiple Imputation
MAR	Missing at Random
MNAR	Missing Not at Random
N/A	Not Applicable
NA	Not Applicable
CCI	
PedsQL™	Pediatric Quality of Life Inventory™
PID(s)	Primary immunodeficiency disease(s)
PK	Pharmacokinetic(s)
PPS	Per-Protocol Set
PT	Preferred Term
QC	Quality Control
QoL	Quality of Life
QTc	Corrected QT Interval
SAE	Serious Adverse Event
SAF	Safety Set
SAP	Statistical Analysis Plan
SD	Standard Deviation
SE	Standard Error
SI	Standard International System of Units
SOC	System Organ Class
SOP	Standard Operating Procedure
TEAE	Treatment Emergent Adverse Event

This document is confidential.

Abbreviation	Description
TLF	Table, Listing and Figure
$t_{1/2}$	Terminal elimination half-life
$t_{max}$	Time to reach maximum concentration
ULOQ	Upper Limit of Quantification
$V_d$	Volume of Distribution (compartmental)
WHO	World Health Organization

This document is confidential.

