### 9.1. PK sampling Schedule

Pharmacokinetic assessments will be performed in approximately [REDACTED] adult patients in order to have 20 evaluable patients before and after the 5th study infusion (28-day infusion schedule) or the 7th study infusion (21-day treatment schedule), when steady state is expected to be achieved (after 5 half-lives of regular infusion of the IMP). Interim PK analysis will be performed when approximately [REDACTED] adult patients (20 evaluable patients) complete intense PK sampling before and after infusion 5 for the 28-day schedule or infusion 7 for 21-day schedule.

Blood samples (approximately 20 mL) will be obtained at the following time-points at 5th (28-day schedule) or 7th (21-day schedule) study infusion:

- 30 minutes to 10 minutes pre-infusion
- 30 minutes ( $\pm$  5 minutes) post-infusion
- 2 hours ( $\pm$  15 minutes) post-infusion
- 24 hours ( $\pm$  2 hours) post-infusion
- 72 hours ( $\pm$  2 hours) post-infusion
- 7 days ( $\pm$  1 day) post-infusion
- 14 days ( $\pm$  1 day) post-infusion
- 21 days ( $\pm$  1 day) post-infusion
- 28 days ( $\pm$  2 days) post-infusion (only for 28 days treatment schedule)

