### 9.2. PK Parameters

Non-compartmental PK parameters will be calculated using Phoenix WinNonlin 8.0 or higher version. Actual sampling times will be used in the determination of the individual PK parameters. Linear up log down method will be used for derivation of AUC.

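### Setting every BLQ value to half the limit conflicts with the SAP's AUC0-t definition and distorts the terminal slope of the specific-antibody curves; the size is conditional

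*SAP*

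**What the plan says.** SAP 9.4.2 introduces its rules with "For calculation of PK parameters, summary statistics and individual serum concentration vs time curves of total IgG" and extends them to IgG subclasses and the three specific antibodies. Rule 3 is "All the BLQ values will be imputed to BLQ/2", with no exception for samples at the end of the curve. Rule 4 sets the only cap: "If there are more than 4 BLQ value in the curve, values will be imputed as above, but no PK parameters will be calculated". SAP 9.1 schedules nine samples for the 28-day regimen and eight for the 21-day regimen, so up to four imputed values can enter the parameters.

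The SAP glossary defines AUC0-t as "Area under the plasma concentration vs. time curve from time 0 to the time t of the last quantifiable concentration". SAP 9.2 adds "Linear up log down method will be used for derivation of AUC".

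SAP 9.3 accepts elimination parameters if adjusted R-squared is at least 0.80 and AUC extrapolation is at most 20%, and leaves flagged values out of summaries. AUC0-t is not among the parameters that can be flagged. Nothing in either document says whether an imputed value counts as quantifiable, or which points enter the terminal slope.

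**The concern.** Read literally, 9.4.2 carries AUC0-t through the imputed tail, while the glossary stops it earlier. Two programmers could deliver different AUC0-t values from the same curve, each following the SAP.

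The slope has its own problem. A true value just under the limit is replaced by half the limit, so the log-concentration falls abruptly at the last point or points. The fitted elimination constant is then too large and the half-life too short.

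PK parameters of anti-Haemophilus influenzae type b, anti-tetanus and anti-pneumococcal antibodies are named endpoints (Protocol 10.4.4, SAP 4.4), summarised by schedule in about 20 evaluable adults. A few affected curves could move a schedule-specific summary.

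**Working it through.** The documents state no half-life or AUC figure to reproduce, so this is a conditional calculation.

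**Inputs**
- Post-infusion sampling times, SAP 9.1: 0.5, 2, 24 and 72 h; 7, 14 and 21 days; 28 days in the 28-day regimen only.
- Half-life: the PK infusion is placed "when steady state is expected to be achieved (after 5 half-lives of regular infusion of the IMP". Week 16 gives 112/5 = 22.4 days (28-day regimen); week 18 gives 126/5 = 25.2 days (21-day regimen). This is an assumption; neither document gives a half-life for any specific antibody.
- Limit: none is given. It is placed anywhere between the true value of the first BLQ sample and the last quantifiable value.
- Curve: noise-free single exponential, C(t) = exp(−kt), k = ln 2 / half-life. AUC is linear-up log-down from the first post-infusion sample.

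**One curve in full (28-day, true half-life 22.4 days, limit crossed on day 25)**
- k = 0.6931/22.4 = 0.03094. True values on days 7, 14, 21, 28: 0.805, 0.648, 0.522, 0.420.
- Limit = exp(−0.03094 × 25) = 0.461. Day 28 is BLQ and becomes 0.231 instead of 0.420.
- Four-point log slope: logs −0.217, −0.433, −0.650, −1.467; centred times ±10.5 and ±3.5; slope = −13.88/245 = −0.0567. Half-life = 0.6931/0.0567 = 12.2 days, adjusted R-squared 0.82.
- AUC to day 21 = 15.42. The imputed segment adds 7 × (0.522 − 0.231)/ln(0.522/0.231) = 2.50, total 17.92. Ratio 17.92/15.42 = 1.16. The true AUC to day 28 is 18.71, so the imputed one is about 4% below truth over the same interval.
- Extrapolation = (0.231/0.0567)/(17.92 + 4.07) = 18.5%. This fit passes both SAP 9.3 criteria. The same curve with no BLQ value extrapolates 42% and fails.

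**Ratio of fitted to true half-life, over all limit positions**

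| Schedule, late BLQ values | last 3 points | last 4 | last 5 |
|---|---|---|---|
| 28-day, one | 0.39–0.48 | 0.51–0.60 | 0.58–0.67 |
| 28-day, two | 0.48–0.62 | 0.51–0.63 | 0.54–0.66 |
| 21-day, one | 0.36–0.43 | 0.44–0.51 | 0.48–0.56 |
| 21-day, two | 0.44–0.55 | 0.43–0.54 | 0.45–0.55 |

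Choosing the points by best adjusted R-squared gives 0.64 to 0.72 in the 28-day regimen with one late BLQ. With three late BLQ values the last three points are equal and give no slope. Four points then give 0.80 to 1.04 in the 28-day regimen, with adjusted R-squared 0.40.

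Over assumed half-lives of 15 to 30 days, with and without an added fast phase, one or two late BLQ values give about 0.31 to 0.93. With three, the ratio can exceed 1 (up to 1.55 at 15 days).

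**AUC0-t with the imputed tail, relative to AUC to the last quantifiable sample**
- 28-day: 16% to 17% higher with one late BLQ, 43% to 49% with two.
- 21-day: 27% to 30% higher with one, about two-fold with two.

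**SAP 9.3 criteria**
- 28-day, one late BLQ: some fits pass both. Besides the example above, a limit crossed on day 23 with three points gives 10.0 days, adjusted R-squared 0.81, extrapolation 16%.
- 28-day, two late BLQ: four-point extrapolation is 21% to 28%, so the fit fails; three-point adjusted R-squared is 0.50.
- 21-day, four points: extrapolation is above 20% in every case.

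**The case against.** A reader might infer that the rule roughly halves the half-life and that the wrong value is then reported as reliable. The documents do not support that as a general statement.

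- Adjusted R-squared is not the only safeguard. The 20% extrapolation limit flags all 28-day four-point fits with two late BLQ values and every 21-day four-point fit. AUC0-inf and volume of distribution would then be left out of summaries. This stands. Whether half-life is also left out is unclear, because SAP 9.3 refers to a third criterion that it does not list and does not say whether failing one criterion alone is enough.
- The size depends on a terminal-point rule the SAP does not give, and three late BLQ values can flatten the slope. This also stands.
- BLQ samples may be rare. Crossing the limit between days 15 and 25 with a 22.4-day half-life means a peak only 1.6 to 2.2 times the limit. Total IgG is unlikely to be affected, since entry requires troughs of at least 6 g/L (SAP 3.5.1), and SAP 9.2.2 plans no PK parameters for subclasses. For specific antibodies the documents say nothing either way.
- The AUC0-t definition is only a glossary entry, and AUCtau does need a value at the end of the interval. Both are fair, but it is the only AUC0-t definition in the SAP, and 9.4.2 makes no exception for it.

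The PK results are descriptive and no efficacy or safety claim rests on them, which limits the consequence but does not remove the conflict.

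**Conclusion.** The concern holds in a conditional form. The conflict between SAP 9.4.2 and the glossary is textual and needs no assumption. It reaches the AUC0-t summaries unfiltered, because SAP 9.3 does not screen that parameter. The AUC0-t excess is a difference between two definitions in the same SAP, not an overestimate of true exposure.

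The slope bias rests on single-exponential decline, the implied half-lives of 22.4 and 25.2 days, and one or two late BLQ samples: about 0.4 to 0.7 of the true half-life. Many such fits would be flagged; some 28-day curves with one late BLQ pass both criteria. How often this would occur cannot be judged from the documents. The point is confined to the specific antibodies and does not touch the primary analysis. It is worth correcting because named endpoints are affected and the correction is small.

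**What to change.** Add to SAP 9.4.2:
- For non-compartmental parameters, BLQ values after the last measured quantifiable sample are treated as missing, are excluded from the terminal slope, and AUC0-t ends at that sample.
- A separate sentence on how AUCtau is completed to the end of the dosing interval when the last sample is BLQ.
- Half the limit is kept for concentration summaries and plots.

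The cost is a few SAP sentences and a standard software setting. In single-exponential curves with enough remaining points the true half-life is recovered. With an assumed fast phase and one late BLQ it is 21.2 against 22.4 days (28-day) and 18.2 against 25.2 days (21-day), so some bias remains.

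The change does not rescue AUC0-inf. In the worked curve, extrapolation from day 21 is (0.522/0.03094)/(15.42 + 16.87) = 52%. Some curves will have too few terminal points or exceed 20% extrapolation, and their elimination parameters and AUC0-inf will not be reported.

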#### 9.4.3. Listing and Presentation of Individual PK Data

Following presentations of individual PK concentrations will be produced:

- Listing of PK sampling times including nominal and actual time elapsed from dose with the deviation from the nominal time and measured concentrations of the drug. The PK samples taken outside the scheduled window will be flagged in listing and can be excluded from summary statistics if the deviation will be deemed to affect the summary result.
- Individual PK profiles in linear scale for all patients within the same dosing schedule combined on one graph and plotted vs. actual time of the samples elapsed from the start of infusion.
- Individual trough concentrations vs. time elapsed from the start of 1st infusion or infusion number.

#### 9.4.4. PK data summarization

- The mean/median value at a time point where 1 or more samples have BLQ values will be reported (in tabular or graphical fashion) even if the mean/median value is BLQ.
- Zero mean or median values will be included in summary tables.
- SD will not be displayed if more than 30% of values are missing or BLQ.

Tables of summary statistics for concentration-time data will report N (number of patients in the analysis population), n (number of actual observations) and the percentage of BLQ values relative to the total number of observations.

Following presentations of mean PK concentrations will be produced:

- Table of PK concentrations summarized by nominal time for each dosing schedule.
- Mean PK profiles in linear and log-linear scale by dosing schedule and plotted vs. nominal time relative to the start of intense sampling infusion
- Median trough concentrations vs. nominal time elapsed from the start of 1st infusion or infusion number by dosing schedule

Pharmacokinetic parameters and serum concentration data will be summarized by each dosing schedule using the following descriptive statistics:

This document is confidential.

Table 1: Concentration Summary Statistics

Variable	Summarized with:
Serum concentration at each time point	n, number and % BLQ, arithmetic mean, SD, coefficient of variance (CV) %, minimum, median and maximum
Continuous PK parameters ( $C_{max}$ , AUCs, ...)	n, arithmetic mean, SD, CV%, minimum, median, maximum, geometric mean and geometric CV%
Categorical PK parameters ( $T_{max}$ )	n, minimum, Q1, median, Q3 and maximum
Semi-continuous PK parameters ( $T_{1/2}$ , $K_{el}$ )	n, arithmetic mean, SD, CV%, minimum, median, maximum

CV% = SD/mean in %.

%BLQ = 100 \* (total number of patients who have BLQ values/total number of patients within each dose level at each time point)

Table 2: Precision of PK Data Reporting

Statistics	Degree of Precision
Minimum, Maximum	3 significant digits or as needed based on actual measured values (for example PK concentrations)
Mean (arithmetic and geometric), Median, Q1, Q3	4 significant digits or as needed based on actual measured values (for example PK concentrations)
SD	5 significant digits or as needed based on actual measured values (for example PK concentrations)
CV% and Geometric CV%	1 decimal place or as needed based on actual measured values (for example PK concentrations)
AUCs, $C_{max}$ , $C_{min}$ , $CL_{ss}$ , $V_d$ , (same for ss parameters) $K_{el}$ , $C_{avg}$ , % fluctuation	4 significant digits
$T_{max}$ , $R^2_{adj}$	2 decimal places
$T_{1/2}$	1 decimal place

CCI

This document is confidential.

CCI

#### 9.6. Comparison of Total IgG trough concentrations

The evaluation of trough concentrations of Total IgG during the study compared to IVIg trough concentrations prior to the study entry will be carried out descriptively, separately for each dosing schedule.

The Total IgG trough concentrations prior to study entry will be compared to the mean of steady state trough concentrations as defined in previous section.

The comparison will be explored graphically using box plots for both dosing schedules separately.

This document is confidential.

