**Investigational Product:**

Kedrion intravenous immunoglobulin (IVIg) 10%

years. The estimate and 1-sided 99% upper confidence limit will be reported. Efficacy will be claimed if this limit is less than 1.0. Supportive and sensitivity analyses will be performed as appropriate. Secondary and exploratory efficacy endpoints will be summarized using descriptive statistics.

Secondary safety endpoints will be summarized using descriptive statistics.

Additionally, a 1-sided 95% confidence interval (CI) will be produced for the proportion of infusions with 1 or more temporally-associated AEs (including AEs determined not to be product-related) using an exact binomial method. Due to the clustered nature of the data, a Design Effect will be applied to the CI. An analysis of variance method will be used to calculate the Intra Cluster Correlation Coefficient (Wu, 2012). For this analysis, safety will be declared if the upper 1-sided 95% confidence is less than **CCI**. Other methods that take in account the clustered nature of the data could be performed (e.g., Generalized Estimating Equation).

Further details will be provided in the SAP.

Pharmacokinetic analysis of total IgG, IgG subclasses, and selected specific IgG antibody levels will be done by non-compartmental analysis. Pharmacokinetic parameters will be derived from serum IgG levels and summarized descriptively, taking into account doses of the drug. Trough levels for all patients will be summarized relative to dosing interval and age category. The frequency of patients with trough concentrations < 6 g/L will be estimated for each infusion number, dose level, and age category, as well as overall. All other data will be reported descriptively. Trough concentrations for total IgG at steady state achieved by the study drug will be compared to IVIg trough concentrations prior to the study entry using statistical model.

Interim PK analysis will be performed when approximately **CCI** adult patients (in order to have 20 evaluable patients) complete intense PK sampling before and after infusion 5 for the 28-day schedule and infusion 7 for the 21-day schedule.

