##### Pharmacokinetic Objectives

To assess the distribution, metabolism, and elimination of Klg10, total IgG, IgG subclasses, and antigen-specific IgGs at steady state in 20 adult PID patients with different dosing schedules.

To evaluate trough concentrations of total IgG and compare to IVIg trough concentrations prior to the study entry.

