#### 5.1 INCLUSION CRITERIA

Patients must meet the following inclusion criteria to be enrolled into the study:

1. Written informed consent/assent obtained from patients/patients' parent(s) or legally acceptable representative indicating that they understand the purpose of and procedures required for the study and are willing to participate in it.
2. Confirmed clinical diagnosis of a PID as defined by 2017 International Union of Immunological Societies (IUIS) Phenotypic Classification for Primary Immunodeficiencies (Bousfiha A, 2018) and requiring treatment with IVIg. Documented agammaglobulinemia (defined as the total absence of one or more

classes of antibodies) or hypogammaglobulinemia (defined as low levels of one or more classes [ie, at least 2 standard deviations under the mean level per age]).

3. Male or female, ages 2 to 70 years at screening.
4. Received 200 to 800 mg/kg of a commercially available IVIg therapy in a range of 21- or 28-day intervals ( $\pm 3$  days or  $\pm 4$  days, respectively) for at least 3 infusion cycles prior to screening.  
(NOTE: Other IVIGs will be prohibited after ICF signature and until study end, week 51/52).
5. At least 2 documented IgG trough levels while receiving an IVIg, of  $\geq 6$  g/L obtained at 2 infusion cycles within 12 months (1 must be within 6 months) prior to ICF signature.
6. Patient (and parent/guardian where applicable) is willing to comply with all requirements of the protocol.
7. Females of child-bearing potential with a negative urine pregnancy test and who agree to employ adequate birth control measures during the study.
8. Authorization to access personal health information.
9. Patients previously participating in a clinical trial with another experimental IVIg may be enrolled if they have received stable commercially available IVIg therapy for at least 3 infusion cycles (21 or 28 days) prior to screening.
10. Patients currently on treatment with any subcutaneous immunoglobulin (SCIG) can be enrolled if they are switched to stable commercially available IVIg therapy for at least 3 infusion cycles (21 or 28 days) prior to screening.

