## 12. Changes from Analysis Planned in Protocol

Not applicable

This document is confidential.

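### The protocol synopsis promises a statistical model for steady-state versus pre-study IgG troughs; SAP 9.6 makes the comparison descriptive, with no named comparator and no interval

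*SAP*

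**What the plan says.** Protocol 3.1 lists as a pharmacokinetic objective: "To evaluate trough concentrations of total IgG and compare to IVIg trough concentrations prior to the study entry". SAP 3.1.3 repeats it unchanged.

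The method appears in the Statistical Analyses part of the protocol synopsis, where steady-state total IgG troughs "will be compared to IVIg trough concentrations prior to the study entry using statistical model". The type of model is not given, and the visible text of protocol 10.4.4 does not repeat the commitment.

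SAP 9.6 says the evaluation "will be carried out descriptively, separately for each dosing schedule". It adds: "The comparison will be explored graphically using box plots for both dosing schedules separately". The two quantities compared are the troughs before study entry, not further identified, and the mean of the steady-state troughs, whose definition lies in the preceding section, which is redacted. SAP 12, on changes from the protocol analysis, reads "Not applicable".

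Three further places matter:

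- SAP 8.2.1 summarises the actual total IgG trough, its change and its relative change from baseline at each visit. SAP 6.2.2 makes baseline the last valid value before the first infusion, normally the Day 1 pre-dose value.
- Protocol 5.1, criterion 5, requires "At least 2 documented IgG trough levels while receiving an IVIg", each of at least 6 g/L, within 12 months before consent (one within 6 months).
- The synopsis says the frequency of patients with troughs below 6 g/L "will be estimated for each infusion number, dose level, and age category, as well as overall".

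**The concern.** A stated objective has one method in the protocol and a weaker one in the SAP, and the SAP section meant to record such differences records none. Under protocol 6.5 patients keep the dose and interval of their previous IVIg, so each is a natural control for himself or herself. Box plots by period do not show within-patient change.

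The comparator is also open. Pre-study trough could mean the two documented historical values, the screening value or the Day 1 pre-infusion value. These differ in laboratory, timing and selection. Left open, the choice can be made after the data are seen.

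At stake is whether the report can state, with its precision, how study troughs relate to those on the earlier product. The primary infection endpoint is not affected.

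**Working it through.** **Passages side by side**

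| Item | Protocol | SAP |
|---|---|---|
| Objective | 3.1: compare with pre-study troughs | 3.1.3: same |
| Method | Synopsis: statistical model | 9.6: descriptive, box plots by schedule |
| Pre-study value | Not specified | Not specified |
| Interval | Not specified | None in visible text |
| Declared change | n/a | 12: none |
| Troughs below 6 g/L | Synopsis: by infusion, dose level, age, overall | 8.2 and 8.2.1: by visit, age, schedule, overall |

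**What SAP 8.2.1 supplies.** The default statistics (SAP 6.1) are n, mean, SD, median, minimum and maximum. For one visit, a reader could build an interval for the mean change as mean ± t × SD/√n. For the average over several steady-state visits this does not work from the tables, because the correlation between visits is not reported. SAP 8 uses the FAS, whereas SAP 9 uses the PK Evaluation Set.

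**Precision of a paired ratio.** The documents give no sample size, variance or margin for this comparison, so there is no plan figure to reproduce. Inputs: n = 20 evaluable adults (protocol 3.1) and an assumed within-patient CV of 10% to 30%. For one trough per period on the log scale, with a true ratio of 1:

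- σw = √ln(1 + CV²): 0.0998 at 10%, 0.2936 at 30%.
- SD of the paired difference = √2 × σw: 0.1411 and 0.4152.
- 90% limits = exp(± t(0.95, n − 1) × √2 × σw / √n).
- n = 20, t = 1.729, CV 10%: exp(± 1.729 × 0.1411 / 4.472) = exp(± 0.0545), giving 0.947 to 1.056.
- n = 20, CV 30%: exp(± 0.1605), giving 0.852 to 1.174.

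If the FAS were used with n = 40, the same formula gives 0.963 to 1.038 at 10% and 0.895 to 1.117 at 30%. For one schedule, assuming an even split of 20 (n = 10, t = 1.833): exp(± 1.833 × 0.1411 / 3.162) gives about 0.92 to 1.09 at 10%, and exp(± 1.833 × 0.4152 / 3.162) gives about 0.79 to 1.27 at 30%. Averaging m steady-state troughs replaces √2 by √(1 + 1/m) if within-patient errors are independent, so these widths err on the wide side under that assumption.

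**Effect of the entry rule, if the documented troughs are the comparator.** Each patient has a true mean trough drawn from a normal distribution (population mean 7 to 10 g/L, between-patient SD 1.5 or 2.5). Two historical values add normal error (SD 0.5 to 1.5), and only patients with both at or above 6 g/L are kept. The true study-to-prior ratio is 1. All of these inputs are assumed. With 1,000,000 simulated patients per scenario:

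| Population mean (g/L) | Upward shift of historical mean (g/L) | Percent |
|---|---|---|
| 7 | 0.031 to 0.433 | 0.4 to 5.5 |
| 8 | 0.020 to 0.268 | 0.2 to 3.1 |
| 9 | 0.008 to 0.154 | 0.1 to 1.6 |
| 10 | 0.002 to 0.099 | 0.0 to 0.9 |

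At the extreme, a true ratio of 1 would read about 1/1.055 = 0.95.

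**The case against.** The strongest reply is that the objective is not left without numbers. SAP 8.2.1 reports within-patient change and relative change from what is normally the Day 1 pre-dose trough, with n and SD, by age, schedule and overall. That stands. A reader might infer from SAP 9.6 that the trial will give no estimate at all; the documents do not support this.

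Second, a reader might infer that the comparator is the set of entry-filtered historical values and that the comparison is therefore biased. SAP 9.6 does not say so. The bias is conditional on that choice, small on the inputs tried, and runs against the study product, so it could not create a favourable result.

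Third, the section before 9.6 is redacted and could hold further trough analysis, including by dose. This limits the dose-level point to the visible text. It does not change the method for this comparison, which 9.6 states itself.

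Fourth, SAP version 4.0 (15 September 2020) follows protocol Version 3, while the protocol here is Version 4 (30 November 2020). It is therefore not shown that SAP 12 was wrong when written. The two documents nevertheless disagree now.

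Last, the protocol names no model, margin or decision rule, so the log scale and the 90% level are choices. Amending the synopsis would also remove the conflict, but it would leave the comparator undefined and the objective without a stated precision.

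**Conclusion.** The point holds in limited form. The synopsis commits to a statistical model for a stated PK objective; SAP 9.6 replaces it with a descriptive comparison, leaves the pre-study trough undefined and gives no interval; SAP 12 does not record the difference. The gap is a prespecified within-patient contrast of mean steady-state trough against pre-study trough with a confidence interval.

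The data would support a useful one: pooled, with 20 patients, roughly ±5% at a within-patient CV of 10%, and about −15% to +17% at 30%, wider by schedule. These widths rest on an assumed CV and independent errors on the log scale. Selection through the entry rule matters only if the documented troughs are used, and is then about 0% to 5.5% on assumed distributions. The change should be made, but it does not bear on the primary efficacy conclusion.

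**What to change.** In SAP 9.6:

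1. Name the Day 1 pre-infusion central-laboratory trough as the main comparator. It is already collected and is not an entry criterion. Keep the documented historical troughs as supportive.
2. State which steady-state visits are averaged, and the analysis set: PK Evaluation Set (about 20 adults) or FAS.
3. Fit a paired or mixed model on log trough and report the geometric mean ratio of mean steady-state to pre-study trough with a 90% CI, pooled and by schedule. Keep the box plots.
4. Add a sensitivity analysis limited to patients whose last prior IVIg was one dosing interval before Day 1.

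Unless the redacted section already covers it, add dose level to the summary of troughs below 6 g/L, as the synopsis states. Correct SAP 12 to list any departure that remains.

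The cost is SAP wording, one model and one table, plus one extra table breakdown. No new data are needed.
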